15.6. Appendix 6: Response Criteria for Multiple Myeloma

Consensus Recommendations [Rajkumar, 2011] for the Uniform Reporting of Clinical Trials: Report of the International Myeloma Working Group (IMWG) Consensus Panel

Response Criteria [Durie, 2006]

sCR (stringent complete response):

Complete response as defined below plus:

- normal free light chain (FLC) ratio and
- absence of clonal cells in bone marrow by immunohistochemistry or 2-4 color flow cytometry.

CR (complete response):

- Negative serum and urine immunofixation, and
- Disappearance of any soft tissue plasmacytomas, and
- $\leq 5\%$ plasma cells in bone marrow.

VGPR (very good partial response):

- Serum and urine M-component detectable by immunofixation but not on electrophoresis **OR**
- 90% or greater reduction in serum M-component plus urine M-component $< 100\text{mg}/24\text{h}$.

PR (partial response):

- $\geq 50\%$ reduction of serum M-protein and reduction in 24 hour urinary M-protein by $\geq 90\%$ or to $< 200\text{mg}/24\text{h}$, and
- If the serum and urine M-protein are not measurable, a $\geq 50\%$ decrease in the difference between involved and uninvolved free light chain levels is required in place of the M-protein criteria. If serum and urine M-protein are not measurable, and serum free light chain assay is also not measurable, $\geq 50\%$ reduction in bone marrow plasma cells is required in place of M-protein, provided baseline bone marrow plasma cell percentage was $\geq 30\%$, and
- In addition to the above listed criteria, if present at baseline, a $\geq 50\%$ reduction in the size of the soft tissue plasmacytomas is also required.

MR (minimal response):

- $\geq 25\%$ but $\leq 49\%$ reduction of serum M-protein and reduction in 24 hour urinary M-protein by 50% to 89%, AND
- If present at baseline, 25% to 49% reduction in the size of soft tissue plasmacytomas is also required.
- No increase in size or number of lytic bone lesions (development of compression fracture does not exclude response).

SD (stable disease):

- Not meeting criteria for CR, VGPR, PR, MR or Progressive Disease.

Progressive Disease:

Requires any one or more of the following:

- Increase of $\geq 25\%$ from lowest response value in any one or more of the following:
 - serum M-component (absolute increase must be ≥ 0.5 g/dl), or
 - urine M-component (absolute increase must be ≥ 200 mg/24h), or
 - the difference between involved and uninvolved free light chain levels (absolute increase must be > 10 mg/dl): only for subjects without measurable serum and urine M-protein levels, or
 - bone marrow plasma cell percentage (the absolute % must be $\geq 10\%$) – only for subjects without measurable serum and urine M-protein levels and without measurable disease by FLC level.
 - definite development of new bone lesions or soft tissue plasmacytomas or definite increase in the size of existing bone lesions or soft tissue plasmacytomas.
 - development of hypercalcemia (corrected calcium > 11.5 mg/dl or 2.65 mmol/l) that can be attributed solely to the plasma cell proliferative disorder.
- a. All response categories (CR, sCR, VGPR, PR, MR and Progressive Disease) require two consecutive assessments made at any time before the institution of any new therapy; CR, sCR, VGPR, PR, MR, and SD categories also require no known evidence of progressive or new bone lesions if radiographic studies were performed. VGPR and CR categories require serum and urine studies regardless of whether disease at baseline was measurable on serum, urine, both, or neither. Radiographic studies are not required to satisfy these response requirements. Bone marrow assessments need not be confirmed. For Progressive Disease, serum M-component increases of more than or equal to 1 g/dL are sufficient to define relapse if starting M-component is ≥ 5 g/dL.
- b. Clarifications to IMWG criteria for coding CR and VGPR in subjects in whom the only measurable disease is by serum FLC levels: CR in such subjects indicates a normal FLC ratio of 0.26 to 1.65 in addition to CR criteria listed above. VGPR in

such subjects requires a > 90% decrease in the difference between involved and unininvolved FLC levels.

- c. Clarifications to IMWG criteria for coding Progressive Disease: Bone marrow criteria for Progressive Disease are to be used only in subjects without measurable disease by M protein and by FLC levels; “25% increase” refers to M protein, FLC, and bone marrow results, and does not refer to bone lesions, soft tissue plasmacytomas, or hypercalcemia and the “lowest response value” does not need to be a confirmed value.

References

Durie BGM, Harousseau J-L, Miguel JS, et. al. International uniform response criteria for multiple myeloma. Leukemia, 2006;20: 1467-73.

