- **STUDY DURATION:** Duration of study will depend on recruitment rates, and timing of subjects' duration on study (withdrawal rates due to toxicity or progression).
- **NUMBER OF SUBJECTS:** Up to approximately 250 subjects worldwide (inclusive both Parts 1 and 2).
- **INCLUSION/EXCLUSION CRITERIA:**

Part I: Inclusion Criteria

Deviations from inclusion criteria are not allowed because they can potentially jeopardize the scientific integrity of the study, regulatory acceptability or subject safety. Therefore, adherence to the criteria as specified in the protocol is essential.

Subjects eligible for enrollment in the study must meet all of the following criteria:

1. Provided signed written informed consent.
2. Males and females ≥ 18 years of age (at the time consent is obtained).
3. Tumor type criteria:
 - Relapsed/refractory NHL that meets the following criteria:
 - Germinal Center B cell Diffuse large B cell lymphoma (GCB-DLBCL) relapsed, or refractory to at least one prior regimen (e.g., rituximab, cyclophosphamide, doxorubicin, vincristine, prednisone [R-CHOP]) AND not a candidate for standard salvage regimens or autologous or allogeneic stem cell transplant. Local confirmation of lymphoma subtype GCB-DLBCL is allowed for enrollment but must be confirmed through central laboratory testing.
 - Solid tumors that meet the following criteria:
 - Measurable disease by RECIST 1.1 in at least 1 site
 - For Castrate Resistant Prostate Cancer (CRPC) measurable disease can also include PSA level (see below)
 - Disease progression with the last line of therapy and at least one prior standard of care regimens, or tumor for which there is no approved therapy, or for which standard therapy is unsuitable or refused.
 - Mutation Status:
 - Solid tumor types, other than prostate, must have one of the following EZH2 inhibitor sensitizing mutations as determined via local testing:

- An activating mutation in EZH2 (Y641F/C/S/H/N, A677V/G, and/or A687V)
 - Loss of a component of the SWI/SNF complex, including, but not limited to, ARID1A, SMARCB1 (aka SNF5/INI1/BAF47), SMARCA4 (aka BRG1), or PBRM1 (aka PB1) as determined by molecular testing (bi-allelic loss or mutation) or immunohistochemistry
 - Loss of BAP1 (ubiquitin carboxy-terminal hydrolase) as determined by molecular testing (bi-allelic loss or mutation) or immunohistochemistry
- CRPC subjects:
 - Must have measurable disease by either:
 - RECIST1.1 ([Appendix 5](#)), or
 - a minimum PSA of 5 ng/mL

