6.3. Permanent Discontinuation from Study Treatment

Subjects will receive study treatment until disease progression, death or unacceptable toxicity, including meeting stopping criteria for liver chemistry defined in Section [8.3.1](#). In addition, study treatment will be permanently discontinued for any of the following reasons:

- Substantial deviation(s) from the protocol
- Request of the subject or proxy (withdrawal of consent by subject or proxy)
- Investigator's discretion
- A dose delay of >21days unless the investigator and GSK Medical Monitor agree that further treatment may benefit the subject
- Intercurrent illness that prevents further administration of study treatment(s)
- Subject is lost to follow-up
- Study is closed or terminated
- Female subject who becomes pregnant while on study treatment

The primary reason study treatment was permanently discontinued must be documented in the subject's medical records and eCRF.

If the subject voluntarily discontinues from treatment due to toxicity, 'adverse event' will be recorded as the primary reason for permanently discontinuation on the eCRF.

Once a subject has permanently discontinued from study treatment, the subject will not be allowed to be retreated.

All subjects who discontinue from study treatment will have safety/disease assessments at the post study treatment Follow Up Visit as specified in the Time and Events Tables.

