7.3.6. Laboratory Assessments

All protocol required laboratory assessments should be performed according to the Time and Events Table (Section 7.1). Details for the preparation and shipment of samples will be provided in the SPM.

Prior to administration of the first dose of study treatment, results of laboratory assessments should be reviewed. Any laboratory test with a value outside the normal range may be repeated (prior to the first dose) at the discretion of the investigator.

If additional non-protocol specified laboratory assessments are performed at the institution's local laboratory and result in a change in patient management or are considered clinically significant by the Investigator (for example SAE or AE or dose modification) the results must be recorded in the subject's CRF. Refer to the SPM for appropriate processing and handling of samples to avoid duplicate and/or additional blood draws.

Abnormal laboratory results that are considered by the investigator to be clinically significant should be recorded on the eCRF as AEs. All laboratory tests with values that are significantly abnormal during participation in the study or within 30 days after the last dose of study treatment should be repeated until the values return to normal or baseline. If such values do not return to normal within a period judged reasonable by the investigator, the etiology should be identified and the sponsor notified.

Hematology, clinical chemistry, urinalysis and additional parameters to be tested are listed below and are to be performed at the institutions local laboratory:

Table 8 List of Clinical Laboratory Tests

Hematology			
Platelet Count	RBC Indices:	Automated WBC Differential:	
RBC Count	MCV	Neutrophils	
WBC Count (absolute)	MCH	Lymphocytes	
Reticulocyte Count	MCHC	Monocytes	
Hemoglobin		Eosinophils	
Hematocrit		Basophils	
Clinical Chemistry			
BUN	Potassium	AST	Total and direct bilirubin
Creatinine	Chloride	ALT	Uric Acid
Sodium	Calcium	Alkaline phosphatase	Total Protein
Magnesium	Glucose	LDH	
FSH and estradiol (as needed in women of non-child bearing potential and all peri menopausal women)			
Pregnancy test for females (serum B-HCG at screening, Urine or serum B-HCG during Continuation Phase)			

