15. APPENDICES

15.1. Appendix 1: COCKCROFT-GAULT FORMULA

$$\text{ClCr (mL/min)} = \frac{Q \times (140 - \text{age[yr]}) \times \text{ideal body weight [kg]}^*}{72 \times \text{serum creatinine [mg/dL]}}$$

Q = 0.85 for females

Q = 1.0 for males

OR

$$\text{ClCr (mL/min)} = \frac{K \times (140 - \text{age[yr]}) \times \text{ideal body weight [kg]}^*}{\text{Serum creatinine [umol/L]}}$$

K = 1.0 for females

K = 1.23 for males

*Calculation of Ideal Body Weight Using the Devine Formula [Devine, 1974]

Ideal body weight:

Males = $50.0 \text{ kg} + (2.3 \text{ kg} \times \text{each inch over 5 feet})$ or $50.0 \text{ kg} + (0.906 \text{ kg} \times \text{each cm over 152.4 cm})$

Females = $45.5 \text{ kg} + (2.3 \text{ kg} \times \text{each inch over 5 feet})$ or $45.5 \text{ kg} + (0.906 \text{ kg} \times \text{each cm over 152.4 cm})$

Example: Male, actual body weight = 90.0 kg, height = 68 inches
Ideal body weight = $50.0 + (2.3) (68-60) = 68.4 \text{ kg}$.

This subject's actual body weight is >30% over ideal body weight. Therefore, in this case, the subject's ideal body weight of 68.4 kg should be used in calculating estimated CrCl.

Reference

Devine, BJ. Case Number 25 Gentamicin Therapy: Clinical Pharmacology Case Studies. Drug Intelligence and Clinical Pharmacy. 1974; 8:650-655.

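### The hypercalcemia limit for myeloma progression is printed as two unequal values: 11.5 mg/dL is 2.87 mmol/L, not 2.65 mmol/L

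*Protocol*

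**What the plan says.** Appendix 6 (Section 15.6) lists the criteria for progressive disease in multiple myeloma, any one of which is enough. One is the "development of hypercalcemia (corrected calcium > 11.5 mg/dl or 2.65 mmol/l"), qualified as hypercalcemia "that can be attributed solely to the plasma cell proliferative disorder". The appendix adds two rules that matter here:

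- Note a: "All response categories (CR, sCR, VGPR, PR, MR and Progressive Disease) require two consecutive assessments".
- Note c says that the 25% increase "does not refer to bone lesions, soft tissue plasmacytomas, or hypercalcemia". The absolute calcium limit therefore carries this criterion without a relative-change test.

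The appendix names no governing unit and gives no conversion. Calcium is in the chemistry panel of Section 7.3.6 (Table 8), whose "parameters to be tested are listed below and are to be performed at the institutions local laboratory". The synopsis plans for "Up to approximately 250 subjects worldwide".

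Progression has consequences elsewhere. Under Section 6.3, "Subjects will receive study treatment until disease progression, death or unacceptable toxicity", and a subject who has permanently discontinued may not be treated again. Section 12.3.5.4 makes progression an event for PFS and the end point of DoR.

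**The concern.** The criterion reads as one cut-off written for laboratories that report in either unit. If the two numbers are not equivalent, the same calcium level can satisfy the criterion or fail it depending only on the unit on the report.

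Reading the word joining the two figures as a literal either/or does not help. The lower limit would then always decide, and the higher figure would do no work.

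What is at stake is the date of progression for some myeloma subjects, and with it PFS, DoR and the length of treatment. Section 6.3 does not allow retreatment, so a discontinuation that followed from the unit could not be reversed by a later analysis rule.

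**Working it through.** **Inputs.** From Appendix 6: 11.5 mg/dL and 2.65 mmol/L. The molar mass of calcium, 40.078 g/mol, is a physical constant that the protocol does not give; values from 40.0 to 40.1 were also tried.

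**Formula.** mmol/L = mg/dL × 10 / molar mass. The inverse is mg/dL = mmol/L × molar mass / 10.

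**Attempt to reproduce the stated equivalence.**

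- 11.5 × 10 / 40.078 = 2.869, so 11.5 mg/dL is 2.87 mmol/L, against the printed 2.65.
- 2.65 × 40.078 / 10 = 10.62, so 2.65 mmol/L is 10.6 mg/dL, against the printed 11.5.

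The equivalence is not reproduced.

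**Size of the gap.**

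- In mg/dL: 11.5 − 10.62 = 0.88.
- In mmol/L: 2.87 − 2.65 = 0.22.
- Relative: 0.88 / 11.5 = 7.6%, with the mmol/L figure the lower of the two.

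**Could something innocent explain it?**

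- Rounding of the first figure: 11.45 to 11.55 mg/dL is 2.857 to 2.882 mmol/L, which does not reach 2.65.
- Rounding of the second figure: 2.645 to 2.655 mmol/L is 10.60 to 10.64 mg/dL, which does not reach 11.5.
- Choice of molar mass: at 40.0 the conversions are 2.875 mmol/L and 10.60 mg/dL; at 40.1 they are 2.868 mmol/L and 10.63 mg/dL. Equality would need 115 / 2.65 = 43.4 g/mol.
- A mislabelled unit: in mEq/L, 11.5 mg/dL is 2 × 115 / 40.078 = 5.74, which does not match either.

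**Who could be scored differently.** All of the following must hold:

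1. The subject has myeloma and corrected calcium between 10.6 and 11.5 mg/dL (2.65 to 2.87 mmol/L).
2. It is in that band on two consecutive assessments.
3. It is attributed solely to the plasma cell disorder.
4. No other progression criterion in Appendix 6 is met.

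Such a subject has progressed under the mmol/L figure and has not under the mg/dL figure.

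**The case against.** The best case on the other side accepts the arithmetic and disputes the reach. Much of it stands.

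- A reader might infer that any corrected calcium between the two limits is progression wherever results come in mmol/L. Appendix 6 does not support that, because sole attribution and two consecutive assessments are also required. A value in the band is necessary, not sufficient.
- A reader might infer that every myeloma subject, up to the 40 planned for Part 2, is affected. That counts the subjects to whom the criterion applies, not those it could misclassify. The protocol gives no rate of isolated hypercalcemia in this band, and the number may be zero. The Part 2 cohort opens only if Part 1 supports it, and myeloma subjects may also enter the dose escalation, so 40 is not the right count in either direction.
- A reader might infer that sites are known to report calcium in different units. No section says so. Local laboratories and worldwide enrollment make it plausible. The two versions of the Cockcroft-Gault formula in Appendix 1 (one uses "Serum creatinine [umol/L") concern creatinine and show nothing about calcium.
- A reader might infer that the primary result is compromised. The Part 2 primary endpoint is ORR, and the myeloma futility rule in Table 18 counts responders only. An early progression call matters there only if it comes before a response that would otherwise have been documented. PFS and DoR are secondary, and are to be calculated only if the data warrant it.

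It may also be said that the pair was taken over from the published consensus criteria that the appendix cites. That cannot be checked here, and an inherited mismatch would still leave investigators with two incompatible limits. Nor is this a detail that can wait for an analysis plan: the protocol itself fixes the numbers that the investigator applies when deciding on progression.

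**Conclusion.** Wrong as written. The two printed limits differ by 0.88 mg/dL (0.22 mmol/L, 7.6%), and neither rounding nor the choice of molar mass closes the gap. The conversion rests only on the molar mass of calcium.

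The practical consequence rests on a further assumption, that laboratories reporting in both units take part. That is an inference. If it holds, the effect is confined to the narrow group defined above and falls mainly on PFS, DoR and time on treatment. The number of such subjects cannot be derived from the protocol and is probably small. The text still needs correcting, because it sets a threshold that can end treatment and the correction is cheap.

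**What to change.** The sponsor should reconcile the two figures in Appendix 6 so that they state one limit with a correct conversion. Two pairs are internally consistent: 11.5 mg/dL with 2.87 mmol/L, or 10.6 mg/dL with 2.65 mmol/L. The protocol does not show which was intended, and this review does not choose between them.

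The cost is one corrected figure in the appendix. No central derivation of the hypercalcemia criterion is needed: Section 7.7 assigns response assessment to the investigator, and sole attribution to myeloma is a judgement that a unit conversion cannot replace.

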15.7. Appendix 7: Criteria for Response/Progression: Prostate Cancer

15.7.1. Disease Progression Endpoint

The disease progression endpoint is defined by 1 or more of the following criteria:

- PSA progression according to the PCWG3 criteria
 - Subjects are not required to discontinue treatment on the basis of meeting PSA progression alone.
 - PSA progression [Scher, 2016] is defined as:
 - *If there has been a decline from baseline:* time from start of therapy to first PSA increase that is $\geq 25\%$ and ≥ 2 ng/mL in absolute value from the nadir, and which is confirmed by a second value 3 or more weeks later (i.e., a confirmed rising trend) at least 9 weeks after the start of treatment
 - *If there has NOT been a decline from baseline:* time from start of therapy to first PSA increase that is $\geq 25\%$ and ≥ 2 ng/mL in absolute value from the baseline value, determined at least 9 weeks after start of treatment
 - Radiographic progression by RECIST 1.1 for subjects with measurable disease.(Appendix 5)
 - Bone progression on bone scan according to the PCWG3 criteria
 - Bone progression [Scher, 2016] will be determined as the appearance of ≥ 2 new lesions on bone scan and at least an additional 2 bone lesions at the next scan (every 8 weeks). The date of progression is the date of the first scan that indicates the change. Subjects should not be discontinued from study treatment(s) due to the occurrence of bone scan changes in the first 12 weeks that do not meet PCWG3 guidelines for progression.

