5.2. Subject Selection Criteria

5.2.1. Part 1 Inclusion Criteria

Deviations from inclusion criteria are not allowed because they can potentially jeopardize the scientific integrity of the study, regulatory acceptability or subject safety. Therefore, adherence to the criteria as specified in the protocol is essential.

Subjects eligible for enrollment in the study must meet all of the following criteria:

1. Provided signed written informed consent.
2. Males and females ≥ 18 years of age (at the time consent is obtained).
3. Tumor type criteria

- Relapsed/refractory non-Hodgkin's lymphoma (NHL) that meets the following criteria:
 - Germinal Center B cell Diffuse large B cell lymphoma (GCB-DLBCL) relapsed or refractory to at least one prior regimen (e.g., rituximab, cyclophosphamide, doxorubicin, vincristine, prednisone [R-CHOP]) AND not a candidate for standard salvage regimens or autologous or allogeneic stem cell transplant. Local confirmation of lymphoma subtype GCB-DLBCL is allowed for enrollment but must be confirmed through central laboratory testing.
- Solid tumors that meet the following criteria:
 - Measurable disease by RECIST 1.1 in at least 1 site
 - For Castrate Resistant Prostate Cancer (CRPC) measurable disease can also include PSA level (see below)
 - Disease progression with the last line of therapy and at least one prior standard of care regimens, or tumor for which there is no approved therapy, or for which standard therapy is unsuitable or refused.
 - Mutation Status:
 - Solid tumor types, other than prostate, must have one of the following EZH2 inhibitor sensitizing mutations as determined via local testing:
 - An activating mutation in EZH2 (Y641F/C/S/H/N, A677V/G, and/or A687V)
 - Loss of a component of the SWI/SNF complex, including, but not limited to, ARID1A, SMARCB1 (aka SNF5/INI1/BAF47), SMARCA4 (aka BRG1), or PBRM1 (aka PB1) as determined by molecular testing (bi-allelic loss or mutation) or immunohistochemistry
 - Loss of BAP1 (ubiquitin carboxy-terminal hydrolase) as determined by molecular testing (bi-allelic loss or mutation) or immunohistochemistry
 - CRPC subjects:
 - Must have measurable disease by either:
 - RECIST1.1 (see [Appendix 5](#)) or,
 - A minimum PSA of 5 ng/mL
 - Disease progression on last line of therapy and must have progressed on abiraterone, enzalutamide, or taxane chemotherapy
 - Subjects may continue GnRH agonists
 - Small cell prostate cancer is eligible

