	STUDY PHASE	SCREEN	First Treatment Period Cycle 1			Day 21	Continuation Phase Cycle 2 and beyond	Follow-Up^j
			Day 1 and 4^a	Day 8 and 11^a	Day 15 and 18^a			
	VISIT	VISIT WINDOW (±days)					±7^l	±7^l
SPEP, FLC assay, quantitative immunoglobulins (IgG, IgA, IgM)	Not required for subjects with non-secretory MM	X					X	
UPEP	Only required if paraprotein is present in urine	X						
Extramedullary Disease Assessment	Only required for MM with extramedullary disease	X						
BM aspirate and biopsy	Required for non-secretory MM, or as appropriate for other subjects	X			Day 18		Week 10, Day 1	
Disease Assessments for Solid Tumors: Baseline disease assessments at screening and repeated every 8 weeks after dosing is initiated								
CT/ Magnetic Resonance Imaging (MRI) ^k	Must be completed within 4 weeks of first dose of GSK2816126 and repeated every 8 weeks	X					X ^d	X ^d

	STUDY PHASE	SCREEN	First Treatment Period Cycle 1			Day 21	Continuation Phase Cycle 2 and beyond	Follow-Up^j
			Day 1 and 4^a	Day 8 and 11^a	Day 15 and 18^a			
	VISIT	Screen						
	VISIT WINDOW (\pmdays)	-14					$\pm 7^l$	$\pm 7^l$
Positron emission tomography (PET)	The use of standalone PET or PET in combination with CT scan is optional. Standalone PET does not replace CT	X ^e					X ^{d, e}	X ^{d, e}
Disease Assessments for Prostate Cancer: (in addition to those assessments for all solid tumor subjects): Baseline disease assessments at screening and repeated as noted below after dosing is initiated								
PSA	Wk 9 and every 4 weeks thereafter	X					X	X
Study Medication								
GSK2816126 Dosing ^a	Dosed 2x weekly with at least 2-3 non-dosing days in between dosing days (3 weeks on/1 week off)							

- a. A subject is to receive two doses per week which should be given with at least 2 non-dosing days in between on the same day of the week during Cycle 1.- If there is a need to change scheduling after Cycle 1, the scheduled days of the week can change as long as there are 2-3non-dosing days between dosing days.

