Ic. Follow-up Assessments for Subjects Permanently Discontinued from Study Treatment

Refer to Section 8.3.1.1 and the Time and Events Tables found in the protocol for follow-up assessment of subjects who are to be followed up for disease progression and/or survival after permanently discontinue from study treatment.

Id. Assessment of Subject Completion

If the last radiographic assessment was more than 8 weeks prior to withdrawal from study and progressive disease has not been documented, a disease assessment should be obtained at the time of withdrawal from study.

II. Guidelines for Evaluation of Disease

IIa. Measurable and Non-measurable Definitions

Measurable lesion:

A non nodal lesion that can be accurately measured in at least one dimension (longest dimension) of

- ≥ 10 mm with MRI or CT when the scan slice thickness is no greater than 5mm. If the slice thickness is greater than 5mm, the minimum size of a measurable lesion must be at least double the slice thickness (e.g., if the slice thickness is 10 mm, a measurable lesion must be ≥ 20 mm).
- ≥ 10 mm calliper/ruler measurement by clinical exam or medical photography.
- ≥ 20 mm by chest x-ray.

Additionally lymph nodes can be considered pathologically enlarged and measurable if

- ≥ 15 mm in the short axis when assessed by CT or MRI (slice thickness recommended to be no more than 5mm). At baseline and follow-up, only the short axis will be measured [Chung, 2010; Eisenhauer, 2009].

Non-measurable lesion:

All other lesions including lesions too small to be considered measurable (longest diameter <10 mm or pathological lymph nodes with ≥ 10 mm and <15 mm short axis) as well as truly non-measurable lesions, which include: leptomeningeal disease, ascites, pleural or pericardial effusions, inflammatory breast disease, lymphangitic involvement of the skin or lung, abdominal masses/abdominal organomegaly identified by physical exam that is not measurable by reproducible imaging techniques [Eisenhauer, 2009].

Measurable disease: The presence of at least one measurable lesion. Palpable lesions that are not measurable by radiologic or photographic evaluations may not be utilized as the only measurable lesion.

Non-Measurable only disease: The presence of only non-measurable lesions. Note: non-measurable only disease is not allowed per protocol.

III. Response Criteria

IIIa. Evaluation of target lesions

Definitions for assessment of response for target lesion(s) are as follows:

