- If a lesion disappears and reappears at a subsequent time point it should continue to be measured. The response at the time when the lesion reappears will depend upon the status of the other lesions. For example, if the disease had reached a CR status then PD would be documented at the time of reappearance. However, if the response status was PR or SD, the diameter of the reappearing lesion should be added to the remaining diameters and response determined based on percent change from baseline and percent change from nadir.

IIIb. Evaluation of non-target lesions

Definitions for assessment of response for non-target lesions are as follows:

- Complete Response (CR): The disappearance of all non-target lesions. All lymph nodes identified as a site of disease at baseline must be non-pathological (e.g. <10 mm short axis).
- Non-CR/Non-PD: The persistence of 1 or more non-target lesion(s) or lymph nodes identified as a site of disease at baseline \geq 10 mm short axis.
- Progressive Disease (PD): Unequivocal progression of existing non-target lesions.

- Not Applicable (NA): No non-target lesions at baseline.
- Not Evaluable (NE): Cannot be classified by one of the four preceding definitions.

Note:

- In the presence of measurable disease, progression on the basis of solely non-target disease requires substantial worsening such that even in the presence of SD or PR in target disease, the overall tumor burden has increased sufficiently to merit discontinuation of therapy.
- Sites of non-target lesions, which are not assessed at a particular timepoint based on the assessment schedule, should be excluded from the response determination (e.g. non-target response does not have to be "Not Evaluable").

IIIc. New lesions

New malignancies denoting disease progression must be unequivocal. Lesions identified in follow-up in an anatomical location not scanned at baseline are considered new lesions.

Any equivocal new lesions should continue to be followed. Treatment can continue at the discretion of the investigator until the next scheduled assessment. If at the next assessment the new lesion is considered to be unequivocal, progression should be documented.

IIId. Evaluation of overall response

The table below presents the overall response at an individual time point for all possible combinations of tumor responses in target and non-target lesions with or without the appearance of new lesions for subjects with measurable disease at baseline.

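### The protocol contradicts itself on how soft-tissue progression is scored in castration-resistant prostate cancer (CRPC) subjects who enter on PSA alone

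*Protocol*

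**What the plan says.** Protocol Section 5.2.1, criterion 3 (repeated in the synopsis), gives CRPC subjects two alternative ways in: RECIST 1.1 disease, or "A minimum PSA of 5 ng/mL". A subject with no measurable lesion can therefore be enrolled.

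Section 15.7.1 (Appendix 7) sets the prostate progression rule: "The disease progression endpoint is defined by 1 or more of the following criteria". The criteria are PSA progression, bone-scan progression, and "Radiographic progression by RECIST 1.1 for subjects with measurable disease", the last with a pointer to Appendix 5.

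Appendix 5 (Section 15.5) defines measurable disease in part IIa as the presence of a measurable lesion, and adds that "non-measurable only disease is not allowed per protocol". Its overall-response table in part IIId covers target and non-target combinations "with or without the appearance of new lesions for subjects with measurable disease at baseline".

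Table 6 in Section 7.1 schedules the prostate assessments "in addition to those assessments for all solid tumor subjects". PSA-entry subjects therefore have CT or MRI every 8 weeks, with PSA at Week 9 and every 4 weeks after that.

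Section 12.3.5.4 refers anti-tumor activity in prostate cancer to Section 15.7. It also defines PFS for the whole study as time to progression on clinical or radiological assessment, or death, with no restriction to measurable disease.

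**The concern.** PSA-entry subjects are scanned on the same calendar as everyone else in the solid-tumor cohort, yet the prostate rule as written has no place for what the scan shows in soft tissue. The eligibility text says that these subjects exist, Appendix 5 says that they do not, Appendix 7 leaves them out of RECIST progression, and the PFS definition counts radiological progression for all.

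Two analysts working faithfully from the same protocol could give one subject two different progression dates from one scan. Within a single small cohort, progression could also be scored by one rule for subjects with a target lesion and another for subjects without.

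This is not a detail that can wait for the analysis plan. Section 12.3.5.4 defers further censoring rules to that plan, but the progression criteria themselves are fixed in the protocol, and they conflict.

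**Working it through.** The plan gives no figure to reproduce. The check compares the passages and then works out the dates.

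**1. A test case.** Take a CRPC subject who enters with PSA of at least 5 ng/mL and no measurable lesion, and whose Week 8 CT shows an unequivocal new liver lesion.

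- *Section 15.7.1, PSA route:* not met by the scan.
- *Section 15.7.1, bone route:* not met. It counts lesions on bone scan only.
- *Section 15.7.1, RECIST route:* closed if measurable disease has its Appendix 5 meaning, because the subject has no measurable lesion.
- *Appendix 5, IIId table:* the row for a new lesion gives progression, but the table is limited to measurable disease at baseline.
- *Appendix 5, IIIc:* treats an unequivocal new malignancy as progression, with no such limit in its own sentence.
- *Section 12.3.5.4:* radiological progression is a PFS event, with no such limit.

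The first four give no progression event at Week 8; the last two give one. Unequivocal growth of non-target disease in the same subject runs into the same conflict: IIIb calls it progression, and 15.7.1 shuts it out.

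**2. The delay if 15.7.1 is followed literally.** Inputs: Table 6 (CT/MRI every 8 weeks; PSA at Weeks 9, 13, 17, and so on) and the PSA rule in 15.7.1 (a rise of at least 25% and at least 2 ng/mL, determined at least 9 weeks after start; measured from nadir with confirmation 3 or more weeks later if PSA has declined, from baseline if it has not). Assumption: nominal visit weeks are weeks since first dose.

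- *No PSA decline:* earliest qualifying PSA is Week 9. Delay = 9 − 8 = 1 week.
- *Decline at Week 9:* earliest rise from nadir is Week 13, confirmed at Week 17 and dated Week 13. Delay = 13 − 8 = 5 weeks.
- *Scan window:* Section 7.7 allows ±7 days, so the scan may fall at Week 7 to 9. With PSA at its nominal date, the delay is 0 to 2 weeks without a decline (9 − 9 to 9 − 7) and 4 to 6 weeks with one (13 − 9 to 13 − 7).
- *No later qualifying PSA, bone event or death:* PFS is censored at the last adequate assessment, and the Week 8 event is lost.

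These are earliest dates; a slower PSA rise lengthens the delay.

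**3. How many subjects.** Section 5.1 plans about 15 subjects in the solid-tumor and prostate expansion together. Neither the prostate share nor the PSA-only share is stated. PSA-only entrants could number anywhere from 0 to about 15, plus any in dose escalation. Part 2 has no prostate cohort. Of the entrants, only those whose soft-tissue disease appears or grows before PSA, bone or clinical progression would be misdated.

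**The case against.** The strongest reply is that the protocol, read as a whole, already counts these events. The PFS definition in 12.3.5.4 is general, and a new metastasis on CT is radiological progression on its face. Appendix 5 has a Not Applicable category for subjects with no target lesions at baseline, an unrestricted new-lesion sentence in IIIc, and a non-target progression rule in IIIb. Criterion 3 also says that for CRPC, measurable disease may include the PSA level, so the phrase in 15.7.1 need not exclude PSA-entry subjects.

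Most of this stands, and it sets the limit of the point. A reader might infer that a new visceral or nodal metastasis is simply not a PFS event in these subjects, and that prostate PFS is therefore biased upward. The documents do not support that: 12.3.5.4 points the other way, and the bias arises only if 15.7.1 is taken as the governing rule. Nor can a 5-week delay be taken as typical, since it needs an initial PSA decline.

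The reply does not remove the conflict. Section 12.3.5.4 names the kind of assessment but sends prostate subjects to 15.7 for the criteria. Section 15.7.1 cites Appendix 5, where measurable disease means lesions, not PSA. If PSA counted as measurable disease throughout, the same phrase in 15.7.2 would bring subjects with no target lesion into the RECIST response analysis, under an appendix that says they are not allowed.

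The second reply, that little depends on prostate PFS, is fair. The cohort is descriptive with no hypothesis, PFS is not among the Part 1 endpoints in Section 2.1, and 12.3.5.4 calculates it only if the data justify it. That lowers the priority but does not settle which rule applies.

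**Conclusion.** The protocol contradicts itself on soft-tissue progression in CRPC subjects who enter on PSA alone. Eligibility admits them, Appendix 5 says they are not allowed, Section 15.7.1 withholds RECIST progression from them, and 12.3.5.4 counts radiological progression for everyone.

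On the literal 15.7.1 reading, a Week 8 soft-tissue event is redated by at least about 1 week without a prior PSA decline, or about 5 weeks after a decline at Week 9, or is lost to censoring. On the 12.3.5.4 reading nothing is lost. The number of subjects exposed is not stated and lies between 0 and about 15 in the expansion cohort, plus any in dose escalation. The direction and size of any effect on reported PFS cannot be established from the protocol.

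This should be corrected because the rule is written down and inconsistent, and because the correction is easy. It does not threaten the study's main conclusions.

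**What to change.** Reconcile the passages for endpoint scoring.

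- **Section 15.7.1:** replace the RECIST bullet with wording such as *Radiographic progression by RECIST 1.1 for all prostate subjects; where there are no target lesions at baseline, unequivocal new lesions or unequivocal non-target progression count.*
- **Appendix 5, IIa:** except CRPC subjects who entered on PSA from the note that bars non-measurable-only disease.
- **Appendix 5, IIId:** state that the new-lesion and non-target progression rows also apply to those subjects, with target response recorded as Not Applicable, a category that Appendix 5 already defines.

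Section 12.3.5.4 then agrees with 15.7.1 as it stands.

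The cost is wording in two appendices. The scans are already scheduled, so no procedure is added. Prostate PFS may come out slightly shorter. Section 6.3 ties continued treatment to disease progression, so the sponsor must also reconcile any consequence for stopping treatment; this point concerns endpoint scoring only and takes no position on that.
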